#### Trial 03-133

As of 30 June 2019, the most common adverse events (AEs) ( $\geq 10\%$ ) were lymphopenia, platelet count decreased, white blood cell count decreased, neutrophil count decreased, vomiting, hemoglobin decreased, cough, headache, contusion, diarrhea, rhinorrhea, decreased appetite, pyrexia, abdominal pain, and nausea. The most common serious adverse events ( $\geq 5\%$ ) were platelet count decreased, neutrophil count decreased, and white blood cell count decreased. Less frequent, but clinically significant serious adverse events ( $< 5\%$ ) include myelodysplastic syndrome, acute myeloid leukemia, seizure, and depressed level of consciousness. 10% of patients discontinued from treatment with I-omburtamab due to adverse events, including decreased platelet count, chemical meningitis, and immune thrombocytopenic purpura. Serious infusion reactions included chemical meningitis, vomiting, pyrexia, headache, and nausea.

## Trial 101

As of 01 Jun 2020, the most common AEs ( $\geq 10\%$ ) were platelet count decreased, white blood cell count decreased, lymphocyte count decreased, neutrophil count decreased, nausea, headache and anemia, vomiting, pain, and pyrexia. The most common serious adverse reaction ( $\geq 10\%$ ) was platelet count decreased. Less frequent, but clinically significant serious AEs related to  $^{131}\text{I}$ -omburtamab administration were chemical meningitis and intracranial hemorrhage. The most common AE leading to discontinuation of  $^{131}\text{I}$ -omburtamab was platelet count decreased. Serious infusion reactions occurred in one patient (chemical meningitis).

## Selected AEs in Trials 03-133 and 101

Myelosuppression is caused by radiation-related adverse effects on the bone marrow and may result in severe and prolonged cytopenia. In Trial 03-133 and Trial 101, a total of 81.7% and 87.5%, respectively, had at least one event related to cytopenia. The most commonly reported hematopoietic cytopenia events were lymphopenia, platelet count decreased, and white blood cell count decreased.

Chemical meningitis is an inflammation of the meninges. Symptoms include fever, headache, nausea, and vomiting. Three patients experienced SAEs of chemical meningitis (2/109 and 1/24 in Trial 03-133 and Trial 101, respectively).

## Serious infusion reactions in Trials 03-133 and 101

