### 3.1.1. Part 1 (Dose-escalation Phase)

Part 1 will comprise 1 dose level consisting of a single patient followed by additional dose levels that use a 3+3 design (see [Figure 1](#)).

In the first 5-week treatment cycle, a 5 mCi dosimetry dose will be administered on Day 1 and a treatment dose (according to the assigned dose level, as listed below) will be administered on Day 8 (see [Figure 1](#) for a schematic of a treatment cycle in Part 1). However, if a patient experiences a Grade 3 or 4 non-hematologic AE (including an AE considered to be a Grade 3 or 4 nervous system disorder) or other DLT after receiving the dosimetry infusion, the treatment dose will not be administered, and the patient will be discontinued from trial treatment. If the dosimetry dose of 5 mCi turns out to deliver a too low acquisition of radioactivity count (see [Section 7.2](#)), the dosimetry dose will be increased to 10 mCi for subsequent patients, at the sponsor's discretion.

A fixed mass dose of approximately 1 mg DTPA-omburtamab will be labelled with increasing radioactivity doses. This mass dose was selected based on the clinical experience with iodine-labelled omburtamab, in which the same mass dose has been shown to be stable and to support clinical use in concentrations up to 100 mCi/ml. The planned radioactivity dose levels are:

- Dose Level 1 (1+2 patients): 10 mCi
- Dose Level 2 (3+3 design): 25 mCi
- Dose Level 3 (3+3 design): 50 mCi
- Dose Level 4 (3+3 design): 65 mCi
- Dose Level 5 (3+3 design): 85 mCi.

A maximum of 1 additional intermediate dose level may be added to the trial if warranted based on the findings from previous dose levels (see [Section 3.1.1.1](#)).

[figure not shown]
Patients who are not discontinued from treatment (according to the criteria in [Section 4.3.2](#)) will be eligible for a second treatment cycle at the same dose administered in the first cycle. The second treatment cycle will not include a dosimetry dose but will instead consist of a treatment dose on Day 1 of the cycle.

In Part 1, the patients will receive a maximum of 2 treatment cycles. Patients who do not experience a DLT will be eligible for Cycle 2 dosing at the same dose administered in Cycle 1. Cycle 2 dosing will not include a dosimetry dose but only a treatment dose on the first day of the cycle.

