### ***3.1.1.2. Definition of Dose-limiting Toxicity***

DLTs are defined as AEs (graded according to CTCAE version 5) occurring within 5 weeks after first IMP administration in Cycle 1 of Part 1 and that are considered possibly or probably related to IMP and meet any of the following criteria:

- Grade 4 myelosuppression (i.e., anemia, thrombocytopenia, or neutropenia) lasting more than 1 week, or more than 3 weeks following intervention (e.g., blood transfusion or granulocyte-macrophage colony-stimulating factor [GM-CSF])
- Any other Grade 4 hematological AE
- Grade  $\geq 3$  thrombocytopenia associated with bleeding
- Grade  $\geq 3$  febrile neutropenia (i.e., fever concurrent with neutropenia) lasting more than 5 days despite use of growth factors and antibiotics
- Grade 4 infusion-related reactions/anaphylaxis
- Grade 3 infusion-related reactions (excluding fever and Grade 3 abnormal laboratory values) that do not resolve to Grade  $\leq 1$  within 5 days of onset.
- Any non-hematological Grade  $\geq 3$  AE that is not listed in the list of exemptions below

DLTs must be entered onto the clinical AE report form and be reported from site to sponsor within 24 hours of the investigator's first knowledge of the event (see [Section 7.4.5.2](#)). If any of the side effects mentioned in the DLT definitions occur during Cycle 2 in Part 1, these will be discussed at the first upcoming preplanned DMC meeting, and the Sponsor Safety Committee will evaluate the DMC recommendations for further dosing.

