### 4.1. Inclusion Criteria

Patients must satisfy all of the following criteria at the Screening Visit, unless otherwise stated:

1. Histologically confirmed diagnosis of medulloblastoma.
2. SHH, Group 3, or Group 4 according to World Health Organization 2016 classification.
3. Recurrent or refractory to frontline therapy, defined as:
  - a. For Part 1 only: Recurrent (maximum of 2 recurrences) or refractory to frontline therapy. Prior frontline or second-line therapy may involve surgery, craniospinal irradiation, stereotactic radiosurgery, and multi-agent chemotherapy regimens.
  - b. For Part 2 only: Recurrent (maximum of 1 recurrence) or refractory to frontline therapy. Patients with recurrent disease must have received second-line chemotherapy for progressive disease. Prior frontline or second-line therapy may involve surgery, craniospinal irradiation, stereotactic radiosurgery, and multi-agent chemotherapy regimens.
4. Have refractory disease, focal or multifocal recurrent disease, or pure leptomeningeal disease. Cytological or radiographic remission is allowed; however, not simultaneously.
5. Performance status score of 50 to 100, both inclusive, on the Lansky [ $<16$  years] or Karnofsky [ $\geq 16$  years] scales.
6. Aged 3 to 19 years, both inclusive, at the time of the first planned dose of trial treatment.
7. Life expectancy of at least 3 months, as judged by the investigator.
8. Acceptable hematological status prior to first dosing (hematological support is allowed if administered at least 1 week before administration of Lu-DTPA-omburtamab), defined as:
  - a. Hemoglobin  $\geq 8$  g/dL
  - b. White blood cell count  $\geq 1000/\mu\text{L}$
  - c. Absolute neutrophil count  $\geq 1000/\mu\text{L}$
  - d. Platelet count  $\geq 75\ 000/\mu\text{L}$ .

9. Acceptable liver function prior to first dosing, defined as:
  - a. Alanine aminotransferase (ALT) and aspartate aminotransferase (AST)  $\leq 5 \times$  upper limit of normal (ULN)
  - b. Bilirubin  $\leq 1.5 \times$  ULN.
10. Acceptable kidney function prior to first dosing, defined as:
  - a. Estimated glomerular filtration rate (eGFR)  $>60$  mL/min/1.73 m^2, calculated by the 2009 revised Bedside Schwartz Equation ([Appendix 4](#)).
11. Written informed consent from legal guardian(s) and/or child obtained in accordance with local regulations. Pediatric patients must provide assent as required by local regulations.

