###### ***4.3.2.1. Discontinuation of Trial Treatment***

Patients may withdraw from the trial treatment at any time at his/her own request or may be discontinued from trial treatment at any time at the discretion of the investigator for safety, behavioral, or administrative reasons. If the patient withdraws consent for disclosure of future information, the sponsor may retain and continue to use any data collected before such a withdrawal of consent. Additionally, patients may request destruction of any samples taken and not tested, and the investigator must document this in the site trial records. Refer to the Schedule of Assessments ([Appendix 3](#)) for data to be collected at the time of treatment discontinuation (EOT visit) and follow-up and for any further evaluations that need to be completed.

The patient must be permanently discontinued from treatment if any of the following occur:

- After receiving the dosimetry dose only, Grade 3 or 4 non-hematologic AE (including an AE considered to be a Grade 3 or 4 nervous system disorder; see [Section 7.1.5](#))
- DLT occurring before the end of Cycle 1 in each dose level in Part 1
- Grade 4 infusion-related reaction/anaphylaxis, or Grade 3 infusion-related reactions (excluding fever and Grade 3 abnormal laboratory values) that do not resolve to Grade  $\leq$  1 within 5 days of onset

- Grade 4 neurological AE
- Development of obstructive or symptomatic communicating hydrocephalus
- Grade 4 treatment-related AEs (excluding infusion-related fever, and non-life-threatening laboratory values)
- Disease progression before Cycle 2 in Part 1 or Cycle 5 in Part 2
- Any medical or safety reason, in the opinion of the investigator or sponsor
- Chemical meningitis (symptoms of clinical meningitis but cultures for infectious agents were negative) in which either: a) event is non-responsive to IV steroids, b) radiologic or operative intervention was indicated, or c) focal neurologic deficit was present
- The patient receives prohibited therapy and/or undergoes procedures during the trial that, in the opinion of the investigator, warrant treatment discontinuation
- Patient decision
- Pregnancy.

A patient who is discontinued from treatment, but for whom consent is not withdrawn, shall continue to be followed for the entire trial period.

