### **5.3.1. Dose Modification**

Dose reductions will not be allowed in Part 1. If a dose reduction is needed in Part 1, the patient should be discontinued from treatment and all EOT Visit assessments completed.

In Part 2, dose reductions in individual patients are permitted where warranted due to toxicity. If dose reduction is needed in Part 2, the reduced dose will be decided upon agreement between the treating investigator and sponsor, guided by the safety and calculated absorbed doses to CSF and blood findings from Part 1.

For patients in Part 1 or 2 presenting with ongoing Grade 3 or 4 myelosuppression in the fifth week of a treatment cycle, and who are otherwise eligible for an additional treatment cycle, a delay of dosing in the next cycle for up to 8 weeks can be introduced, provided that the myelosuppression has sufficiently declined to Grade  $\leq 2$ . Dose delay will be enforced at the discretion of the treating investigator.

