 The Lu-DTPA-omburtamab Treatment Period is divided into 5-week cycles. In Part 2, a cycle consists of a treatment dose on Day 1. The patient can receive up to 5 cycles at the discretion of the investigator. The infusion reservoir must be flushed with HSA and CSF after each infusion. The patient will be observed post treatment to decide if further cycles can be administered.

Day 1, 15, and 29 for Cycles 2 to 5 correspond to Day 36, 50, and 64 (for Cycle 2), Day 71, 85, 99 (for Cycle 3), 106, 120, 134 (for Cycle 4), and 141, 155, and 169 (for Cycle 5). Adjustments to the dosing schedule will be accommodated on a patient-by-patient basis depending on the clinical condition of the patient.

 If the IMP is discontinued prior to completion of all scheduled visits of the cycle (i.e., up to and including Day 29), the treatment visits that fall after the date of the EOT Visit should be skipped, and the patient should move directly into the follow-up phase. If the IMP is discontinued after Cycle 1, an unscheduled visit (including MRI etc.) should be done at 13 weeks post first dose.

 All patients who are dosed with Lu-DTPA-omburtamab in Part 2 should be followed up regularly (every 13 [±2] weeks, i.e., 26, 39, and 52 weeks post first dose, then every 26 [±2] weeks, i.e., 78 and 104 weeks post first dose, and thereafter annually) for monitoring of secondary malignancies during the trial and for at least 10 years after the end of trial, or until death, if sooner.

 Informed consent must be obtained before any trial-related procedures. If the indwelling ICV access device (e.g., Ommaya) is placed in connection with the tumor resection, the informed consent must be obtained prior to the surgery, and before the start of the screening period, unless this is placed as part of a standard of care procedure at site. If any procedures/tests are from before informed consent is obtained, it must be clear from source documents that this was not performed for the purpose of the present trial. In these cases, the procedures/tests do not need to be repeated at the Screening Visit if they were performed within the allowed timelines. The investigator is responsible for documenting this properly.

 Only anti-cancer therapy.

 Physical examinations to be performed at screening and as clinically indicated.

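### Section 5.3.1 leaves redosing during ongoing Grade 3–4 myelosuppression to discretion and does not make recovery to Grade ≤2 a condition of the next dose

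*Combined protocol and SAP*

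**What the plan says.** Section 5.3.1 (Dose Modification) holds the only redosing rule for low counts, and it covers both parts. For a patient with ongoing Grade 3 or 4 myelosuppression in the fifth week of a cycle who is otherwise eligible for another, "a delay of dosing in the next cycle for up to 8 weeks can be introduced, provided that the myelosuppression has sufficiently declined to Grade" 2 or lower. The paragraph closes: "Dose delay will be enforced at the discretion of the treating investigator".

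Other sections bear on the same decision:

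- **Section 3.1.1**, for Part 1: "Patients who do not experience a DLT will be eligible for Cycle 2 dosing at the same dose administered in Cycle 1". Section 5.1 says much the same for both parts, for any patient not discontinued.
- **Section 4.1**, criterion 8, sets limits for hemoglobin, white cells, neutrophils and platelets under the words "Acceptable hematological status prior to first dosing". It accepts hematological support only if given at least 1 week before dosing.
- **Table 8**, footnote 1, for Part 2: "The patient will be observed post treatment to decide if further cycles can be administered".
- **Section 4.3.2.1** requires permanent discontinuation for a DLT in Part 1 Cycle 1 and for related Grade 4 AEs, but the latter item exempts laboratory values that are not life-threatening. It also has a general item: "Any medical or safety reason, in the opinion of the investigator or sponsor".
- **Section 3.1.1.2** counts as a DLT "Grade 4 myelosuppression (i.e., anemia, thrombocytopenia, or neutropenia) lasting more than 1 week, or more than 3 weeks following intervention".

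**The concern.** Marrow toxicity is the effect this protocol most expects. Of the iodine-131 product, Section 1.2.1 says: "Myelosuppression is caused by radiation-related adverse effects on the bone marrow and may result in severe and prolonged cytopenia". Sections 3.2 and 3.3.3 tie the 10 mCi starting dose to myelosuppression seen in mice. The rule for redosing after low counts therefore carries real weight, and as written it does not settle the case it was written for.

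Two things are at stake. The first is patient safety: one investigator may redose a child on unrecovered marrow while another holds, and both comply. The second is the evidence. Section 3.1.2 lets toxicity accumulated over two cycles lower the RP2D, and Section 4.4 uses Cycle 1 and 2 toxicity to judge whether five cycles are feasible. If sites redose under different policies, cumulative toxicity partly reflects those policies. In Part 2 the one planned DMC meeting comes when the eighth patient has completed Cycle 1 dosing, so no review is scheduled for the later cycles, although event-triggered review under Section 4.4.1 remains.

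**Working it through.** The plan states no figure for this rule, so the check is mainly a comparison of texts, with some schedule arithmetic.

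**1. Section 5.3.1 on its own terms.** The trigger is ongoing Grade 3 or 4. The delay is permissive and left to discretion. Grade ≤2 is attached to introducing the delay. A patient who meets the trigger fails the condition, so the sentence taken literally cannot be applied. The workable reading is that the next dose may be given up to 8 weeks late once counts are Grade ≤2. The text does not say that, and it does not say when the 8 weeks start.

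**2. Whether another section supplies the rule.**

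| Section | What it contributes | What it leaves open |
|---|---|---|
| 4.1, criterion 8 | Fixed count limits, 1 week free of support | First dose only |
| 3.1.1 and 5.1 | Eligibility for the next cycle | No count condition |
| 3.1.1.2 with 4.3.2.1 | A Part 1 Cycle 1 DLT ends treatment | Uncomplicated Grade 3; Grade 4 anemia, thrombocytopenia or neutropenia of up to 1 week, or up to 3 weeks following intervention; all of Part 2 |
| 4.3.2.1, related Grade 4 AEs | Ends treatment in either part | Grade 3; laboratory values that are not life-threatening |
| 4.3.2.1, general safety item | Ends treatment on opinion | No common standard |
| Table 8, footnote 1 | Observation before further cycles | No threshold |
| Tables 7 and 8 | Hematology on Day 1 of each cycle | No threshold attached to the result |

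None of these makes Grade ≤2 a condition of redosing, and no item in Section 4.3.2.1 names failure to recover within 8 weeks.

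**3. What remains.** In Part 1 it is mainly Grade 3 cytopenia and short Grade 4 cytopenia. In Part 2 it is Grade 3 and non-life-threatening Grade 4 counts ahead of Cycles 2 to 5.

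**4. Timing.** In Part 1 the Cycle 1 treatment dose is on Day 8, and Cycle 2 starts 35 days after the Day 1 dosimetry dose, on Day 1 + 35 = 36.

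- Part 1, dose to dose: 36 − 8 = 28 days. With a full delay of 8 × 7 = 56 days: 28 + 56 = 84 days.
- Part 2, dose to dose: 36 − 1 = 35 days. With a full delay: 35 + 56 = 91 days.
- Week 5 of Part 1 Cycle 1 (Days 29 to 35) lies 29 − 8 = 21 to 35 − 8 = 27 days after the treatment dose.

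The 84 and 91 days assume that the delay runs from the planned dosing day.

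**5. Ceiling on the decisions governed.** Part 1: up to 25 patients × (2 − 1) = 25. Part 2: 24 patients × (5 − 1) = 96. Together 25 + 96 = 121 redosing decisions at most, over about 9 + 2 = 11 sites. Only those with Grade 3–4 counts in week 5 are affected, and the documents give no rate for them.

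**The case against.** The strongest reply is that the intent is plain. Section 5.3.1 speaks of patients who are otherwise eligible, which treats the myelosuppression as the obstacle to dosing. Eight weeks is a cap and Grade ≤2 a condition, so a patient who meets neither has no evident route to another dose. Adjusting the schedule to the individual patient is a stated choice (Section 3.1 and the schedule footnotes), Part 2 permits dose reduction, and the general safety item is always available. The protocol also reports that myelosuppression with the iodine-131 product was not dose-limiting (Section 1.2.3) and that acute hematological toxicity was manageable (Section 3.3.3).

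Much of this stands. A hold is implied, and the Grade 4 and DLT stops narrow the gap. But an implied hold followed by a sentence giving the delay to the investigator's discretion is not a requirement, and the general safety item rests on opinion.

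Three stronger readings are tempting and are not supported:

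- **That the protocol permits free redosing on Grade 4 marrow.** Section 4.3.2.1 already ends treatment for Part 1 Cycle 1 DLTs and, in both parts, for related Grade 4 events outside its exemptions.
- **That DLT classification, and so the MTD, is undermined.** A Grade 4 count starting on Days 29 to 35 has not lasted more than 1 week by Day 36. Without intervention it first does so on Days 29 + 8 = 37 to 35 + 8 = 43. Redosing on Day 36 could blur its duration, but only for late onset and an investigator who doses through it. The DMC makes the final DLT assessment, so the event stays assessable. This is marginal.
- **That most patients would be affected.** Section 1.2.1 gives 81.7% and 87.5% with any cytopenia event in the two iodine-131 trials. Those figures are not limited to Grade 3–4 or to week 5.

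**Conclusion.** The point holds in a bounded form. Section 5.3.1 makes the delay discretionary, attaches its recovery condition to the wrong act, and states no outcome for counts still above Grade 2 after 8 weeks. A site that redoses at Grade 3, or at a Grade 4 count outside the existing stops, has broken no stated rule. The size is set by the cases left open in step 3 of the working and cannot be expressed as a rate. This is a correction the sponsor should make because it is cheap and concerns the main expected toxicity. It is not a flaw that invalidates the escalation or the expansion. The conclusion rests on reading the intended rule as hold, then redose at Grade ≤2.

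**What to change.** Replace the last paragraph of Section 5.3.1 with:

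> If anemia, thrombocytopenia or neutropenia is Grade 3 or 4 in the fifth week of a cycle or at the pre-dose count, the next dose must be held. It is given only when all three are Grade ≤2 without hematological support in the preceding week (as in inclusion criterion 8), and no later than 8 weeks after the planned dosing day; otherwise trial treatment is permanently discontinued.

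Add the matching item to Section 4.3.2.1 and leave the existing Grade 4 and DLT stops unchanged. A patient back at Grade ≤2 by the planned day, without support in the preceding week, is dosed on time. The support-free week is needed because Section 6.3 allows blood products and growth factors, which could otherwise lift a count just before dosing. Starting the 8 weeks at the planned dosing day is an assumption for the sponsor to confirm.

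State that the pre-dose count comes before dosing: the footnote saying so stands under Table 6 and is not repeated under Tables 7 or 8. Where feasible, take it before the IMP dose is ordered or drawn up, because Section 5.2 has the product prepared on demand.

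The cost is protocol wording, lost discretion to redose at Grade 3–4, lost later cycles for patients not recovered by 8 weeks, a few extra local counts (Section 7 allows unscheduled safety samples), and occasionally a wasted prepared dose.
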